5.12.4 Recording YSI Results

The YSI source documents will be labeled as follows throughout the study to facilitate matching glucose results on the source document with results recorded on the CRF:

Sample identification will include:

- 1) Ascensia serum traceability control level or
- 2) Subject ID plus either 'capillary' or 'venous' blood

NOTE: If glucose results are not to be used due to operator errors, insufficient sample, etc., this should be clearly marked on the YSI source document.

The YSI operator or designee will label all samples on YSI tape and record YSI results for all plasma and control sample runs on the appropriate source documents.

The YSI operator will record all non-numeric codes - QNS (Quantity not sufficient), NO (Not Obtainable), and error codes as appropriate for the YSI tests.

5.13 Subject Questionnaires

Site staff will administer two questionnaires to subjects. Questionnaire 1 will be given to all subjects and Questionnaire 2 will be given only to subjects with diabetes.

5.13.1 ***Questionnaire 1: Evaluation of Instructions for Use. (All subjects)***

Staff will administer a questionnaire to all subjects who perform fingerstick self-testing after the individual meter testing is completed.

The questionnaire will include statements for which a numerical score or rating will be provided by subjects (1=strongly disagree, 2=disagree, 3=neutral, 4=agree, 5=strongly agree). These numerically scored statements will be tabulated into frequency distributions. The following statements will be subject to the pass/fail criteria listed in the study objectives section:

- I find it easy to do a fingerstick blood test with this meter.
- The meter display is easy to see and read.
- It was easy to understand my test results.
- The instructions (User Guide and Quick Reference Guide) were easy to understand.
- The instructions clearly explain how to run a test.
- The instructions clearly explain what to do if an error message is displayed by the meter. *Note: an error message will be demonstrated by the study staff if the subject does not experience an error message during his/her testing.*

Per ISO 15197:2013, Section 8.8.2, the questionnaire will also contain a section whereby the subject can provide unrestricted comments on their experience about using the BGMS. This questionnaire will be administered by the staff who will record the subject's responses. The subject will be given an example questionnaire to assist with providing the responses.

5.13.2 ***Questionnaire 2: BGMS Features. (Only subjects with diabetes)***

After all testing and the first questionnaire have been completed, the study staff will demonstrate to only the subjects with diabetes several features of the BGMS that would not necessarily be experienced during the brief accuracy testing. This will ensure that the subjects are able to understand the features, and answer questions in the questionnaire.

There are no acceptance criteria for this questionnaire. This questionnaire may be 1) administered by the staff who will record the subject's responses or 2) completed by the subjects and verified by the study staff, as per site procedures. In the first scenario, the subject will be given an example questionnaire to assist with providing the responses.

5.14 Procedures repeated on BGMS 2

After completing study procedures for the first BGMS randomly-assigned to them, subjects will then repeat all of these procedures using the second BGMS, except the hematocrit and venipuncture procedures. (Hematocrit is measured on a separate instrument and is not meter-

specific; venipuncture is performed once and measured on both meters, as previously described.) Therefore, for BGMS 2, subjects will complete a fingerstick test; a YSI sample will be collected by a Tenderlett stick from subject; subject will complete a palm AST; study staff will perform a fingerstick test from the subject; study staff will administer Questionnaire 1; and, if the subject has diabetes, study staff will administer Questionnaire 2.

Table 5.2 – Subject Testing Schematic

Step	BGMS	Test type	Operator	Description
1	1	Fingerstick Self-test	Subject	
 ▪ Subject lances finger – Microlet NEXT lancing device. ▪ Test meter with 1 lot of test strip (Repeat 2 more times, only if needed). ▪ Record time of successful meter test.
2	1	Tenderlett deep stick	Study staff	
 ▪ Immediately following Step 1 meter test (≤ 5 min), staff lances subject fingertip (up to 3 lancements allowed). ▪ Record time of lancing. ▪ Collect blood in Li Heparin tube (approx. 200 – 300 uL). ▪ Centrifuge blood and record time (should be within 15 min of meter test in step 1).
3	1	AST palm Self-test	Subject	
 ▪ Immediately following Step 2, subject lances palm – Microlet NEXT lancing device. ▪ Test with same test strip lot and meter as above. (Repeat 2 more times, only if needed.) ▪ Record time of successful meter test (should be within 15 min of centrifugation in Step 2).
4	1	Study staff test	Study staff	
 ▪ Immediately following Step 3, staff lances subject fingertip - Microlet NEXT lancing device. ▪ Test with same test strip lot and meter as above. (Repeat 2 more times, only if needed.) ▪ Record time of successful meter test (should be within 15 min of centrifugation in Step 2).
5	1 then 2	Venous test (only subjects with diabetes)	Study staff	
 ▪ May be done prior to Steps 1-4. ▪ Staff performs venipuncture on subjects with diabetes (up to 3 attempts allowed). ▪ Collect blood in 4 ml Vacutainer tube with heparin anticoagulant. ▪ Staff tests blood (out of view of subject) with same meter and strip lot as fingerstick test. ▪ Centrifuge blood and record time (should be within 15 min of venous blood meter test).
6	na	Hematocrit	Study staff	
 ▪ Fill 2 microhematocrit tubes (only 1 tube to be measured). ▪ Blood is from capillary or venous blood.
7	na	Questionnaire 1	Study staff	
 ▪ Study staff administers Questionnaire 1 to all subjects.
8	na	Questionnaire 2 (only subjects with diabetes)	Study staff	
 ▪ Study staff demonstrates BGMS features to subjects with diabetes. ▪ Study staff administers Questionnaire 2 to subjects with diabetes.
9-14	2	all	all	
 ▪ Repeat steps 1 – 4 (meter tests) and 7-8 (questionnaires) with BGMS 2.

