- 2.2.2 Subject Questionnaire 1: The questionnaire will include statements about the BGMS instructions for use (product labeling) and ease of use of the basic blood testing operations of the meter system. These statements will be given a rating by all of the subjects (1=strongly disagree, 2=disagree, 3=neutral, 4=agree, 5=strongly agree), and frequency distributions will be tabulated. Results will be compared to the following criteria:
- **Acceptance criteria: At least 90% of the applicable statement responses from the questionnaire must be ≥ 3 to pass*.**

Study objectives 2.3.1 and 2.3.4 below are in accordance with **ISO 15197:2013, Section 8**, and apply to data collected **ONLY** from **subjects who have diabetes**. Objectives 2.3.2 and 2.3.3 also apply to subjects who have diabetes. The objectives apply to both CONTOUR NEXT and CONTOUR TV3 BGMS, and the results from the two meter systems will not be compared to each other.

2.3 Secondary Objectives, only subjects with diabetes:

- 2.3.1 Fingerstick Test: Obtain BGMS performance data in the hands of lay users with diabetes using fingerstick capillary blood obtained with Microlet NEXT lancing device.
- **95% of glucose results shall fall within ± 15 mg/dL of laboratory method at glucose concentration < 100 mg/dL and within $\pm 15\%$ at glucose concentrations ≥ 100 mg/dL**
- 2.3.2 Alternative Site Test (AST): Obtain BGMS performance data in the hands of lay users with diabetes using capillary blood from the palm site obtained with Microlet NEXT lancing device with the AST endcap. Acceptance criteria will be the same as fingerstick 2.3.1.
- 2.3.3 Venous Blood Test: Obtain BGMS performance data using venous blood from lay users with diabetes. Acceptance criteria will be the same as fingerstick 2.3.1.
- 2.3.4 Subject Questionnaire 1: The questionnaire will include statements about the BGMS instructions for use (product labeling) and ease of use of the basic blood testing operations of the meter system. These statements will be given a rating by the subjects with diabetes (1=strongly disagree, 2=disagree, 3=neutral, 4=agree, 5=strongly agree), and frequency distributions will be tabulated. Results will be compared to the following criteria:

*This is a “total population” (hypothesis test) requirement for the pool of all subjects.

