- **Acceptance criteria: There must be at least a 90% probability that a user would respond with a score of 3 or higher to statements concerning instructions for use or ease of use.****

Study objectives 2.4 below are internal objectives and apply to data collected from all subjects OR subjects who have diabetes, as specified for each objective. The objectives apply to CONTOUR NEXT and CONTOUR TV3 BGMS as noted, and the results from the two meter systems will not be compared to each other.

2.4 Secondary Objectives (internal objectives):

2.4.1 Fingerstick Test (only subjects with diabetes): Obtain BGMS performance data in the hands of lay users with diabetes using fingerstick capillary blood obtained with Microlet NEXT lancing device.

CONTOUR NEXT:

- **95% of glucose results shall fall within ± 10.5 mg/dL of laboratory method at glucose concentrations < 100 mg/dL and within $\pm 10.5\%$ at glucose concentrations ≥ 100 mg/dL****

CONTOUR TV3:

- **95% of glucose results shall fall within ± 12.5 mg/dL of laboratory method at glucose concentrations < 100 mg/dL and within $\pm 12.5\%$ at glucose concentrations ≥ 100 mg/dL****

2.4.2 Study staff test (both BGMS; two analyses, one for all subjects and one for only subjects with diabetes): Obtain BGMS performance data in the hands of trained study staff testing subjects' fingerstick blood obtained with Microlet NEXT lancing device.

- **95% of glucose results shall fall within ± 15 mg/dL of laboratory method at glucose concentrations < 100 mg/dL and within $\pm 15\%$ at glucose concentrations ≥ 100 mg/dL*,****

2.4.3 Subject Questionnaire 2 (both BGMS; only subjects with diabetes): This questionnaire for subjects with diabetes will include statements about user preferences and feedback regarding the features of the BGMS in routine diabetes management. These statements will be given a rating by the subjects (1=strongly disagree, 2=disagree, 3=neutral, 4=agree, 5=strongly agree), and frequency distributions will be tabulated.

- **Acceptance criteria: There are no pass/fail criteria for Questionnaire 2.**

**This is a "total population" (hypothesis test) requirement for the pool of all subjects with diabetes.

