4.0 Subject Recruitment, Inclusion/Exclusion Criteria

Subject Recruitment: At least 370 subjects will be enrolled into the study. These will be people with diabetes (type 1 or type 2) and a smaller number, 10 - 15%, without diabetes. The subjects will be members of the local communities.

4.1 Inclusion Criteria:

- 4.1.1 Males and females, 18 years of age and older
- 4.1.2 Ability to speak, read and understand English. Subjects must demonstrate ability to read a paragraph from the first page of the UG to qualify for the study.
- 4.1.3 Willing to complete all study procedures

4.2 Exclusion Criteria:

- 4.2.1 Hemophilia or any other bleeding disorder
- 4.2.2 Pregnancy (self-reported)
- 4.2.3 Physical, visual or neurological impairments that would make the person unable to perform testing with the BGMS.
- 4.2.4 Previous participation in a blood glucose monitoring study using the Ascensia CONTOUR NEXT or CONTOUR TV3 BGMS.
- 4.2.5 Working for a medical laboratory, hospital or other clinical setting that involves training on or clinical use of blood glucose monitors.

4.2.6 Working for a competitive medical device company, or having an immediate family member or someone who is not a family member but is living within the household of someone who works for such a company.

- Immediate family members are the subject's parents, spouse, children, and siblings, including the parent's spouse; step-children and adopted children and their spouses.
- A competitive medical device company is a company that provides a medical device or components of a device that is related to diabetes.

For example, people who are not eligible are those who work for companies that create or manufacture the following (or a company that is in a partnership with a company that provides such devices): lancing devices, blood glucose monitoring systems, continuous glucose monitoring systems, insulin pens, or systems related to the measurement of HbA1c.

People who are eligible are those who work for companies associated with products such as wound dressings, medications or dietary products.

4.2.7 A condition, which in the opinion of the investigator or designee, would put the person or study conduct at risk. The reason for exclusion will be clearly documented by investigator or designee on the subject disposition form.

4.3 **General Enrollment Details - Combined across sites**

4.3.1 The following additional population criteria are study goals with each site recruiting to meet these goals:

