$$H_0: Pr\{response \geq 3\} < 90\% \text{ versus the alternative:}$$

$$H_a: Pr\{response \geq 3\} \geq 90\%$$

The critical number of responses greater than or equal to 3, X_c , is a function of the actual sample size, and will be chosen such that $0.95 = \sup Pr\{X \geq X_c | 100p\% = 90\%\}$. For example, if $n = 350$, then $X_c = 307$, so that $Pr\{X \geq X_c | 100p\% = 90\%\} \approx 0.9316 \leq 0.95$. That is, 307 is the number of responses ≥ 3 which yields the largest value of $Pr\{X \geq X_c | 100p\% = 90\%\} \leq 0.95$ for $n = 350$. For $n = 315$, the critical value is $X_c = 300$ (power ≈ 0.95).

11.4 Demographic, Diabetes History, Medications and Medical Conditions Data, Questionnaires 1 and 2

Descriptive statistics for Demographics, Diabetes History, Medications and Medical Conditions, and subject questionnaires will be computed as appropriate. Histograms will be constructed where appropriate. A percentage of subjects < 65 years of age will be calculated.

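### Questionnaire 1, the only questionnaire with acceptance criteria, must be administered and recorded by study staff, which leaves an absolute pass mark open to a possible upward bias

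*Combined protocol and SAP*

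**What the plan says.** **Questionnaire 1.** Section 5.13.1 lists six statements on ease of use and clarity of the instructions and adds: "The following statements will be subject to the pass/fail criteria listed in the study objectives section". On mode it says "This questionnaire will be administered by the staff who will record the" subject's answers, with an example form given to the subject as an aid. Section 5.14 and Table 5.2 (step 7, repeated for the second meter) also have staff administer it. Section 3.0 says only that subjects complete it, without saying who writes the answers down.

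**Its criteria.** Objective 2.2.2 (all subjects): "At least 90% of the applicable statement responses from the questionnaire must be" 3 or more. Objective 2.3.4 (subjects with diabetes): "There must be at least a 90% probability that a user would respond with a score of 3 or higher". Both are secondary objectives and apply to each meter.

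**Questionnaire 2.** Objective 2.4.3: "There are no pass/fail criteria for Questionnaire 2". Section 5.13.2 allows two modes: administered and recorded by staff, or "completed by the subjects and verified by the study staff, as per site procedures".

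**Literacy.** Inclusion criterion 4.1.2: "Subjects must demonstrate ability to read a paragraph from the first page of the UG to qualify for the study".

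No reason is given for the difference in mode. For Questionnaire 1 the protocol describes no neutral script, independent interviewer or concealed recording.

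**The concern.** The mode that keeps staff out of the rating is open only to the questionnaire without a criterion. For the one that is scored pass or fail, each rating of the sponsor's meter and instructions reaches the data through a member of the study staff. A subject who is reluctant to criticise in front of staff would tend to choose 3 or more, which is the definition of success, so the plausible direction of bias favours passing.

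The criterion is an absolute 90% proportion. The two meters are not compared with each other, and there is no control arm in which the same reluctance would appear and cancel. Any upward drift goes straight into the pass decision. Questionnaire 1 serves an FDA objective and an ISO objective for each meter, so it bears on all four planned reports.

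**Working it through.** **Inputs**
- All subjects: n = 350, critical value Xc = 307, threshold rate 90% (section 11.3 and Table 11.1).
- Subjects with diabetes: n = 315, Xc = 276, threshold rate 90% (Table 11.1).
- True proportion p of subjects scoring 3 or more: not given, so a range is shown.
- Size of any interviewer effect: not given, so a range is shown.

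**Formula.** For one statement, P(pass) = P(X ≥ Xc), where X is binomial(n, p). One statement is modelled because section 11.3 describes tests for selected statements with n equal to the number of subjects.

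**The plan's own figure.** P(X ≥ 307 | 350, 0.90) = 0.9316, as section 11.3 prints. Xc = 306 gives 0.9510, so 307 is the smallest value with a pass chance of at most 0.95, which is the stated rule.

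**Which value for n = 315.** The documents print two. Table 11.1 gives 276 and section 11.3 gives 300. At p = 0.90, 276 gives 0.9299 and 275 gives 0.9505, so 276 follows the rule. A value of 300 gives 0.0005 and does not. The figures below use 276.

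**Pass chance by true rate**

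| True rate | 307 of 350 | 276 of 315 |
|---|---|---|
| 84% | 0.03 | 0.04 |
| 86% | 0.20 | 0.23 |
| 87% | 0.38 | 0.41 |
| 88% | 0.61 | 0.62 |
| 89% | 0.81 | 0.81 |
| 90% | 0.93 | 0.93 |
| 91% | 0.98 | 0.98 |
| 92% | 0.998 | 0.997 |
| 95% | 1.00 | 1.00 |

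**Reading it as a shift (n = 350)**
- 2 points: 86 to 88% moves 0.20 to 0.61; 87 to 89% moves 0.38 to 0.81; 88 to 90% moves 0.61 to 0.93.
- 3 points: 86 to 89% moves 0.20 to 0.81; 87 to 90% moves 0.38 to 0.93.
- 4 points: 86 to 90% moves 0.20 to 0.93; 87 to 91% moves 0.38 to 0.98.

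**Reading it as softened answers.** Suppose a share s of subjects who truly rate below 3 report 3 or more. The reported rate is then q = p + (1 − p)s. At p = 0.86:
- s = 0.10: q = 0.86 + 0.14 × 0.10 = 0.874. Pass chance 0.47 (n = 350) and 0.50 (n = 315).
- s = 0.20: q = 0.86 + 0.14 × 0.20 = 0.888. Pass chance 0.77 and 0.78.

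In head counts, 0.14 × 350 = 49 subjects are truly unfavourable, and s = 0.20 means about 10 of them soften the answer.

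**The case against.** **A single mandatory mode is defensible.** It standardises the scored instrument across sites and supports complete data, whereas Questionnaire 2 varies with site procedures. This does not settle the matter, because mandatory self-completion at both sites is just as standardised and a completeness check deals with skipped items.

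**The example form is a safeguard.** The subject can read the statements and the scale. That stands as partial protection, but the rating is still given to staff and written by them.

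**The effect may be nil.** A neutral 3 counts as success, so only active disagreement counts against the meter. If the true rate is 92% or more, the pass chance is already at least 0.997 and bias changes nothing. This stands: the documents show exposure and neither its size nor an expected rate.

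**The remedy is partial.** Staff would still see the form, and they demonstrate the error message behind one scored statement when none has occurred. Reading one paragraph of the User Guide supports literacy but does not prove that every subject can complete the form unaided. All of this stands.

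**A source may prescribe the mode.** Section 5.13.1 cites the ISO standard only for the free-comment section. Whether that standard addresses mode cannot be checked from the documents.

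**Readings to avoid.** A reader might infer that subjects must voice disagreement face to face to the person who ran their tests. The text says only that staff administer and record; it does not say that answers are spoken or that the administrator is the tester. Nor would the interviewers be sponsor representatives, whom section 5.17 bars from interacting with subjects.

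**Conclusion.** The point holds as a design weakness that is cheap to reduce. Staff recording is mandatory where a criterion applies and optional where none does, without a stated reason, and any resulting bias would probably favour passing.

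Its size is conditional. It matters only if the true proportion lies a few points below 90%. From 86% or 87%, an upward shift of about 3 to 4 points turns a probable fail (0.20 or 0.38) into a likely pass (0.81 to 0.93, or 0.98 for the full 4 points from 87%). At 92% or above the verdict would not change. These figures assume one statement, independent subjects, the sample sizes in Table 11.1 and, for n = 315, the critical value of 276.

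A reader might go further and infer that a 2-point shift turns a fail into a near-certain pass. It does not: from 86% or 87% it reaches only 0.61 or 0.81, and at 88% the pass is already more likely than not. Nor do the documents show that bias will occur, or that the primary accuracy objective is affected. The criteria concerned are secondary.

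**What to change.** In section 5.13.1, section 5.14 and Table 5.2 step 7 (with its repeat for the second meter), have the subject complete the numerically scored Questionnaire 1 statements in writing, at both sites and for both meters. Staff check only that every item is answered. They may still record the free comments and demonstrate the error message. Section 11.3, which has ratings entered by staff, should be worded to match. While editing that section, reconcile its critical value of 300 for n = 315 with the 276 in Table 11.1.

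The cost is protocol wording and use of the questionnaire as a subject-completed form. The downsides are an occasional skipped or unclear item, which the completeness check should mostly catch, and some remaining exposure because staff still handle the completed form.

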1.0 Background Information

CONTOUR[®] NEXT is the proposed name of a blood glucose monitoring system (BGMS) consisting of a new meter and marketed CONTOUR NEXT[®] test strip. The development name of the meter is LIGHTNING NEXT. CONTOUR TV3 is the proposed name of a BGMS consisting of a new meter and new V3 test strips. The development name of the meter is THUNDER TV3. The meters can wirelessly transmit BG results using Bluetooth Low Energy to the CONTOUR mobile application that will be available on specified versions of the iOS and Android mobile platforms.

This clinical trial will assess the performance (accuracy) of the CONTOUR NEXT and CONTOUR TV3 meters by lay users enrolled as subjects in the study, and by health care professionals (also called study staff). The trial will follow the requirements and procedures described in FDA Guidance on Self-monitoring Blood Glucose Test Systems: 2016 (FDA SMBG:2016)¹ and ISO 15197:2013 International Standard, Section 8². Results will be evaluated and reported for each of the two BGMS according to each of the two standards (FDA and ISO), for a total of four reports. CONTOUR NEXT results and CONTOUR TV3 results will not be compared to one another.

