3.0 Study Design Summary

This study was designed to satisfy both the *FDA SMBG:2016* and the *ISO 15197:2013, Section 8* requirements. Besides different analysis criteria, the main difference between these regulations is that FDA SMBG:2016 requires that both naïve users (people without diabetes) and people with diabetes are included in the study population. The ISO 15197:2013 standard states that the study population shall be people with diabetes.

The study will be conducted at two clinical sites and enroll a total of approximately 370 lay users. Ten to fifteen percent (10 - 15%) of the enrolled subjects will be people without diabetes and the remaining subjects will be people with diabetes.

For this study, there must be at least 350 total evaluable fingerstick self-test results and at least 350 total evaluable AST palm self-test results for each BGMS, CONTOUR NEXT and CONTOUR TV3. In addition, per FDA SMBG:2016, at least 10 unaltered fingerstick blood samples will be < 80 mg/dL and 10 will be > 250 mg/dL. Subject enrollment will continue until the required evaluable samples are collected.

Sites are not required to replace subjects with diabetes who did not have evaluable venous blood results.

The subjects will be 18 years and older. Each subject will make one visit, lasting approximately 2 hours, to the clinical trial site. Study sessions will be conducted by study staff members who have been trained on all aspects of the protocol, forms, the use of the CONTOUR NEXT and CONTOUR TV3 systems, data collection, and GCP.

All subjects will complete the informed consent process before performing any study procedures.

Procedures - All Subjects

According to a randomization schedule, subjects will be assigned to: 1) use either the CONTOUR NEXT or CONTOUR TV3 meter first, and 2) use one of three test strip lots corresponding to each meter throughout the visit.

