The untrained subjects, who have never used either of the systems previously, will be sequestered in such a way that they cannot observe or be influenced by the testing technique of other study participants. They will learn to use the assigned meter by reading the corresponding User Guide (UG) and Quick Reference Guide (QRG). Each subject will perform one fingerstick self-test using a Microlet NEXT or similar lancing device and the assigned meter. Immediately following the subject self-test, a Tenderlett™ or similar device will be used by the study staff on the subject's finger (same hand) to collect a capillary sample for testing on the YSI Glucose Analyzer.

Immediately following the Tenderlett lancing, subjects will lance their palm using the Microlet NEXT lancing device (with AST clear endcap) and will perform a self-test using the meter.

Immediately following the AST test, the staff person will perform a fingerstick test on the subject. All subject self-test results and study staff results will be compared to YSI results from blood obtained from the Tenderlett fingerstick.

Hematocrit will be measured for all subjects.

All Subjects will then complete a questionnaire (Questionnaire 1) to provide feedback on the meter system and instructions for use (UG and QRG).

Procedures - Only Subjects with Diabetes

Subjects with diabetes will be given a venipuncture. The venous blood will be tested by the study staff using the CONTOUR NEXT and CONTOUR TV3 systems, maintaining randomized first meter order, and the YSI lab analyzer. The venipuncture may be performed any time after the subject is enrolled (i.e. completed informed consent and passed inclusion/exclusion criteria).

After all testing is completed, staff will demonstrate to the subjects with diabetes several features of the meter system that would not necessarily be experienced during the brief accuracy testing. These subjects will be given a second questionnaire (Questionnaire 2) to provide feedback about the new features of the system.

Procedures repeated with second BGMS

After completing study procedures for one BGMS, subjects will then repeat all of these procedures using the second BGMS, except the hematocrit and venipuncture procedures. (Hematocrit is measured on a separate instrument and is not meter-specific; venipuncture is performed once and measured on both meters, as previously described.)

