5.6 Subject Enrollment

- 5.6.1 At least 185 untrained subjects, who have never previously used the Ascensia CONTOUR NEXT or CONTOUR TV3 BGMS, should be enrolled into the study at each site in order to have a total of at least **350 evaluable fingerstick** and **350 evaluable AST palm** blood results for each BGMS. Of the fingerstick blood samples, 10 samples should be < 80 mg/dL and 10 samples > 250 mg/dL (by YSI assay). If this requirement is not achieved with 350 subjects, additional subjects should be enrolled to meet this fingerstick requirement. Note that the goal at each site should be approximately five capillary fingerstick blood results < 80 mg/dL and five > 250 mg/dL.
- 5.6.2 The site study staff will perform the following when the subject arrives at the clinical trial site:
 1. Complete the informed consent process.
 2. Assign a unique number to each subject.
- 5.6.3 The study staff will document subject demographics (including both screen-failed and enrolled subjects), diabetes history, medical conditions and medications information.

Subjects will also be asked when they last ate, took diabetes medications, and performed vigorous exercise.

5.6.4 If the subject does not have diabetes, the outside of the subject folder will be labeled to indicate that venipuncture should NOT be performed.

5.6.5 According to a randomization schedule, subjects will be assigned to: 1) use either the CONTOUR NEXT or CONTOUR TV3 meter first, and 2) use one of three test strip lots corresponding to the meter throughout the visit (lot R, B, or G).

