5.7.2 AST (palm) testing

1. Only proceed to AST testing if an adequate blood sample is obtained from Tenderlett lancing for YSI analysis.
2. The same meter and test strip lot used for fingerstick testing will be used for AST testing.
3. Immediately following Step 5.7.1, the subject will perform an AST (palm) stick using the lancing device (new lancet), preferably on the same hand as the fingerstick lancing, and test his/her blood on Meter 1.
4. If adequate blood is not obtained from the Microlet palm lancements for the meter test, up to 2 additional Microlet palm lancements are allowed (total of up to 3 AST palm lancements).
5. The time of the successful AST meter test will be recorded. The time interval between the blood centrifugation and the AST meter test should be as soon as possible, and within 15 minutes or less.
6. If the time from meter test to blood centrifugation exceeds 15 minutes, the test is considered non-evaluable. This will not be considered a protocol deviation. Times of meter tests and centrifugation will be recorded.

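### Does each meter's pass rate need a breakdown by meter order, given that about half of its results follow a session on the other meter?

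*Combined protocol and SAP*

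**What the plan says.** Section 3.0 describes the participants as "The untrained subjects, who have never used either of the systems previously", and Section 5.6.1 sets recruitment per site as "At least 185 untrained subjects, who have never previously used the Ascensia CONTOUR NEXT or CONTOUR TV3 BGMS". Exclusion 4.2.4 is "Previous participation in a blood glucose monitoring study using the Ascensia CONTOUR NEXT or CONTOUR TV3 BGMS".

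By the schedule in Sections 3.0 and 5.6.5, each subject is assigned to "use either the CONTOUR NEXT or CONTOUR TV3 meter first". Section 5.14 then states: "After completing study procedures for the first BGMS randomly-assigned to them, subjects will then repeat all of these procedures using the second BGMS" (hematocrit and venipuncture excepted). Table 5.2, steps 9-14, gives the same sequence: "Repeat steps 1 – 4 (meter tests) and 7-8 (questionnaires) with BGMS 2".

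Section 1.0 adds that "CONTOUR NEXT results and CONTOUR TV3 results will not be compared to one another", and Section 11.0 analyses each meter independently. Accuracy tables are by site and combined. The study staff test and Questionnaire 1 are also split into all subjects and subjects with diabetes. Meter order appears in no table, plot, test or listing in Section 11. Section 11.8 sends supplemental or unplanned analyses to a supplemental report.

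**The concern.** The plan takes care over prior exposure: it enrols people new to both systems, sequesters them and gives no training. Yet by the time a subject picks up the second meter, he or she has normally self-tested finger and palm on the first, had a staff fingerstick on it, answered Questionnaire 1 and seen an error message, by demonstration if none occurred. Someone in second position is no longer new to both systems.

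Randomising the order would balance any carry-over in a comparison of the meters, but none is made. Each meter faces its own cut-off (333/350 within 15%, 347/350 within 20%), so a learning or fatigue effect stays in its pooled proportion. Questionnaire 1, which has pass/fail criteria, is exposed in the same way. If second-position results were better, a meter that performs poorly in new users could pass; if worse, a good meter could fail. The plan specifies no table that would show either.

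**Working it through.** **Inputs.** From Section 11.1: n = 350; cut-off 333 with P0 = 96.65% and Pa = 92.81%; cut-off 347 with P0 = 99.61% and Pa = 97.80%. Assumed: 1:1 order, so 350/2 = 175 per position. All second-position rates below are illustrations; the documents give none.

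**The plan's own figures.** Exact binomial tails:

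- P(Bin(350, 0.9665) ≥ 333) = 0.950; P(Bin(350, 0.9281) ≥ 333) = 0.050
- P(Bin(350, 0.9961) ≥ 347) = 0.950; P(Bin(350, 0.9780) ≥ 347) = 0.050

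All agree with Section 11.1.

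**What carry-over could do.** Pass probability = P(Bin(175, p1) + Bin(175, p2) ≥ cut-off), by exact convolution, where p1 is the first-position rate and p2 the second. The last column is the exact probability that a Newcombe 95% interval for the second-minus-first difference, 175 per position, excludes zero.

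| Cut-off | p1 | p2 | Gap (points) | P(pass) | P(interval excludes 0) |
|---|---|---|---|---|---|
| 333 | 92.81% | 92.81% | 0 | 0.05 | – |
| 333 | 92.81% | 93.81% | +1.00 | 0.10 | 0.06 |
| 333 | 92.81% | 95% | +2.19 | 0.20 | 0.13 |
| 333 | 92.81% | 97% | +4.19 | 0.48 | 0.42 |
| 333 | 92.81% | 99% | +6.19 | 0.81 | 0.87 |
| 333 | 96.65% | 95% | −1.65 | 0.79 | 0.11 |
| 333 | 96.65% | 94% | −2.65 | 0.63 | 0.20 |
| 333 | 96.65% | 92.81% | −3.84 | 0.42 | 0.35 |
| 347 | 97.80% | 99% | +1.20 | 0.19 | not computed |

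If the order split were 60:40 either way (140 to 210 second-position results), the 0.20 in the third row would run from 0.16 to 0.25.

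**What the missing table could show.** With no order effect at 96.65%, the half-width of the difference is 1.96 × √(2 × 0.9665 × 0.0335 / 175) = 0.038; the Newcombe half-width for 169/175 in both positions is 0.043. A gap of 2 to 4 points, large enough to matter for the pass rule, would usually be missed. Nor could the first-position half be held to 95% by itself: 0.95 × 175 = 166.25, so 167 are needed, and with no order effect at 96.65% it would miss with probability P(Bin(175, 0.9665) ≤ 166) = 0.135.

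**Is a first-ever test what the plan estimates?** Set side by side:

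- The wording about using neither system sits in the description of participants, the enrolment target and an exclusion. These describe people at entry.
- The objectives in Section 2 ask for performance in the hands of lay users. Naïve there means without diabetes, not new to meters.
- Section 4.2 bars earlier study use of these two systems and occupational exposure to glucose meters. It does not bar users of other home meters, although 85-90% of subjects have diabetes.
- Practice within the visit is accepted elsewhere. On the palm test: "Immediately following Step 5.7.1, the subject will perform an AST (palm) stick using the lancing device (new lancet"). That test always follows a finger self-test on the same meter, yet Section 2.2.1 gives it the fingerstick criteria.
- Section 5.10 allows up to three attempts after error codes and repeats when the subject feels an error was made. A first-position result need not be a first attempt.
- A second-position subject has still not used the meter now being tested, has its own guides and receives no training.

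**The case for a change.** The best case for a change is that it costs almost nothing. Order is a randomised factor known for every subject; one descriptive table per meter and one listing column need no new subjects or procedures. Prespecifying them would put the check in the main reports and avoid a choice made after the data are seen. The plan's own care over exposure suggests that exposure matters, and the pass probabilities above move a good deal once gaps exceed about 2 points.

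The factual part stands: the mix of positions is real, randomised order does not remove it from a single-meter result, and Section 11 is silent on it. The table would be harmless as optional description.

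The step from there to a needed change does not stand. The large shifts in pass probability come from assumed gaps, in most rows with first position set at a rate the plan already treats as failing. The table would judge nothing, and its likeliest result, an interval spanning zero, would not settle the question. The shared lancing device is a plausible route for carry-over, but nothing in the documents shows that one session on another meter differs materially from the home-meter experience the plan already admits.

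**Conclusion.** No change is needed. About 175 of 350 self-test results per meter are second-position if order is 1:1 (140 to 210 if the split were 60:40 either way), and nothing is tabulated by order. But the pooled proportion still answers the stated objective, performance in lay users enrolled without experience of either system, and the critical values and pass probabilities in Section 11.1 are unaffected. No bias is shown in either direction. A breakdown by position would have a half-width of about 4 points, would detect gaps of 2.2 to 4.2 points with probability 0.13 to 0.42 (first position at 92.81%), and would change no decision.

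An analyst who wants the table can build it from the randomisation schedule and recorded test times, and Section 11.8 provides for it in a supplemental report. The groups are then better called first and second position than first and second use. The conclusion rests on reading the never-used condition as an entry criterion. Had an objective required first-ever use of any such system, second-position data would not meet it.
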